6.0 STATISTICAL ANALYSIS

6.1 Primary and secondary endpoints.

The primary endpoint is difference in caregiver anxiety between the intervention and control groups at 20

weeks post-radiation treatment. Secondary endpoints are caregiver anxiety at the end of radiation treatment and 4 weeks post treatment; caregiver depression, HRQOL, and fatigue at the end of treatment and 4 weeks post-treatment; and patient HRQOL at the end of treatment and 4 weeks post-treatment.

6.2, 6.7, 6.8 Statistical Design, Power, Analysis plan, & Missing data.

An intent-to-treat analysis is planned. Before carrying out inferential statistical procedures, exploratory data analysis will be performed: all variable distributions will be examined and descriptive summary statistics will be provided: including means, standard deviations, and ranges for continuous variables, as well as percentages and frequencies for categorical variables, will be provided to describe the study sample. Variable transformations will be made in cases where distributions are skewed, or otherwise fail to meet the assumptions for analyses; nonparametric procedures will be used where transformations would be inappropriate. Plots will be used to describe the data and identify outliers and influential observations.

Aim 1

Analysis. The primary analysis for Aim 1 will be to compare the control and CG intervention arms with respect to CG anxiety at T4 (20 weeks postradiation treatment). A linear mixed model repeated measures analysis will be used to obtain mean changes from baseline in anxiety scores at Times T2, T3, and T4, using baseline anxiety as a covariate, also adjusting for covariates described in Table 4. A contrast of means will be constructed to compare arms with respect to change in anxiety at T4 (primary analysis) at the 0.05 significance level. In addition, the baseline characteristics of the two treatment groups will be compared using appropriate 2-sample tests for continuous or binary outcomes, and in a secondary analysis, characteristics found to differ between groups at baseline will be adjusted for in the linear mixed model. A secondary analysis will test for differences between groups at the other postbaseline time points, using the Tukey method to control the familywise error rate on a per outcome basis. Other CG outcomes will be compared between groups using a similar approach.

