Power. With 180 subjects randomized and a 10% dropout rate, the sample size for the primary analysis will be 162 CGs (81 per arm). Assuming a correlation of 0.50 between CG anxiety scores at baseline and T4, when adjusting for baseline anxiety, a difference in means of 0.36 standard deviations (*SDs*) can be detected with 80% power using a 2-sided test with significance level 0.05, where *SD* is the within-group standard deviation of anxiety scores at Time T4. Here, adjustment for baseline anxiety reduces the detectable effect size from 0.41 to 0.36. This effect size (Cohen's *d*) is intermediate between a "small" (0.2) and "moderate" effect size, as defined by Cohen,¹⁰⁶ and is close to the pooled estimate of 0.29 from a meta-analysis of interventions (psychoeducational, skills training, and therapeutic counseling) with family CGs of cancer patients.² For other outcomes, there is 80% power to detect effect sizes of 0.41 *SDs* with a 2-sided test, significance level 0.05.

Aim 2

Analysis. This aim is to measure the effect of the intervention, as compared to a control group, on patient outcomes (HRQOL, interrupted treatment course) and healthcare utilization outcomes (unplanned hospital admissions, unplanned emergency room visits, and unplanned IV fluid use). Most outcomes will be count variables enumerating the cumulative numbers at T2, T3, and T4, which can be analyzed using Poisson regression methods implemented as generalized linear models, possibly allowing for overdispersion. Zero-inflated Poisson or negative binomial models^{107,108} will be considered if the data indicate a higher frequency of zeros than predicted by a Poisson model. HRQOL, a continuous measure, will be analyzed using a linear mixed model with repeated measures at T1, T2, T3, and T4. We will analyze the effect of the intervention on HRQOL across diagnoses using the common FACT subscales and will describe the symptom experience within each diagnostic group using the cancer-specific FACT subscale.

Power. From our pilot study, in the control group we expect means of 0.29 and 0.25 for the number of unplanned missed days and number of unplanned hospital admissions, respectively. In a Poisson regression model, sample sizes of 81 patients per group will provide 80% power to detect a 68% reduction in unplanned missed days and a 72% reduction in unplanned hospital admissions in the intervention group compared to the control group (2-sided test, significance level 0.05).

Aim 3

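### The Tukey method named for the T2 and T3 arm comparisons does not match two planned contrasts; on its most natural reading it is valid but stricter than needed

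*Combined protocol and SAP*

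**What the plan says.** Section 6.0 of the combined protocol and SAP, Aim 1 Analysis, fits a linear mixed model to caregiver anxiety at T2, T3 and T4 with baseline as a covariate. The primary contrast is to "compare arms with respect to change in anxiety at T4 (primary analysis) at the 0.05 significance level". The next step reads: "A secondary analysis will test for differences between groups at the other postbaseline time points". Its multiplicity rule is given as "using the Tukey method to control the familywise error rate on a per outcome basis". The other caregiver outcomes are to be handled in a similar way.

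Section 6.1 names the same two visits. "Secondary endpoints are caregiver anxiety at the end of radiation treatment and 4 weeks post treatment", and the list continues with "caregiver depression, HRQOL, and fatigue at the end of treatment and 4 weeks post-treatment".

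The trial has two arms (Section 5.1). The plan sets the family at the level of the outcome. It does not say which means, or which pairs of means, enter the Tukey procedure.

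**The concern.** With two arms and two visits, each caregiver outcome has two planned comparisons: intervention against control at T2, and again at T3. Tukey's procedure is built for all pairs among k means. Applied to the four arm-by-visit means, it also allows for changes over time within an arm and for one arm at T2 against the other at T3. The sentence plans neither.

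The price is power in the secondary tests. T2 matters to the investigators: Section 5.1 explains that they chose the end of radiation so as to compare groups when side effects are intense. Because the means are not listed, two analysts could also use different thresholds. A T2 p-value of 0.03 would pass Holm's or Tukey's test under one implementation and fail under another.

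**Working it through.** **1. The plan's own power figures.** Aim 1 Power gives 0.41 SD (unadjusted) and 0.36 SD (baseline-adjusted) at 80% power, two-sided 0.05, 81 per arm. It rests on this: "Assuming a correlation of 0.50 between CG anxiety scores at baseline and T4". Detectable difference = (1.960 + 0.842) × √(2/n) × √(1 − ρ²).
- n = 81: 0.440 SD with ρ = 0; 0.381 SD with ρ = 0.5.
- n = 90 (all 180 randomized): 0.418 and 0.362 SD.

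The stated figures are therefore close to what 90 per arm gives, not 81. That is a separate matter. What counts here is that they use a plain 0.05, with no multiplicity adjustment.

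**2. Number of contrasts.** Three post-baseline visits less T4 leaves T2 and T3: two contrasts per outcome.

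**3. Critical values.** Tukey's critical |t| is q(0.95; k, df)/√2.
- k = 4 (two arms × T2, T3; 4 × 3/2 = 6 pairs), df 212: 3.662/1.414 = 2.590, a per-contrast alpha of 0.0103. At df 160 it is 2.596.
- Bonferroni for two contrasts, alpha 0.025 each: 2.257 (df 212) to 2.263 (df 160).
- Multivariate-t (max-t) for two contrasts, df 200: 2.253 at contrast correlation 0, falling to 2.168 at 0.8. The correlation is not in the documents, so a range is shown.

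**4. Familywise error over the T2 and T3 contrasts.** Simulated with 40,000 null data sets per setting, 107 per arm, baseline correlation 0.5, and an assumed T2-T3 correlation of 0.4 / 0.6 / 0.8:
- Tukey k = 4: 0.021 / 0.019 / 0.017
- Holm: 0.049 / 0.046 / 0.041

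**5. Per-contrast power.** Noncentral t with noncentrality d / (√(1 − 0.5²) × √(2/n)). For example, n = 107 and d = 0.36 give 0.36/(0.866 × 0.1367) = 3.04. The 107 assumes a 1:1 split of the 214 in Section 3.0, Projected Enrollment. The plan gives no T2 or T3 effect size or correlation. The 0.5 correlation and 0.36 SD are borrowed from the T4 power statement; 0.29 SD is the meta-analytic effect cited there, of which the plan says its target "is close to the pooled estimate of 0.29 from a meta-analysis of interventions"; 0.50 SD is added to show a larger effect.

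| n per arm | Effect (SD) | Bonferroni, 2.26 | max-t, 2.21 | Tukey k = 4, 2.59 |
|---|---|---|---|---|
| 107 | 0.29 | 0.577 | 0.595 | 0.445 |
| 107 | 0.36 | 0.783 | 0.796 | 0.673 |
| 107 | 0.50 | 0.975 | 0.977 | 0.948 |
| 81 | 0.36 | 0.649 | 0.668 | 0.523 |

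The value 2.21 lies inside the max-t range of step 3. Holm's simulated per-contrast power at 107 per arm is 0.58 (effect at one visit) or 0.63 (effect at both) at 0.29 SD, 0.78 or 0.82-0.83 at 0.36 SD, and 0.98 or 0.98-0.99 at 0.50 SD.

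**6. Tukey within each visit (k = 2).** 2.788/1.414 = 1.971, the ordinary t critical value. There is then no adjustment across visits. Error over two independent contrasts would be 1 − 0.95² = 0.0975; the simulation of step 4 gives 0.097 / 0.092 / 0.081.

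**The case against.** The strongest reply is that the plan promises familywise control per outcome, and Tukey over the four T2/T3 means delivers it. A conservative procedure for secondary tests is not an error, and the loss depends on effect sizes that nobody has specified for these visits: it is about 3 points at 0.50 SD. This largely stands. It limits the point to one of fit and efficiency, and the borrowed inputs are assumptions.

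A reader might infer three stronger things, none of which the documents support.
- *That secondary error is inflated to 8-10%.* This happens only if Tukey is run separately within each visit. The per-outcome wording goes against that: it would be a misimplementation contrary to the stated aim.
- *That Tukey runs over all six post-baseline means, T4 included, with a larger loss.* The sentence is confined to the visits other than T4, so this could come only from a software default.
- *That the family is wholly undefined.* Its level, the outcome, is stated. What is missing is the list of means or contrasts.

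The reply does not dispose of the mismatch itself. No set of means makes Tukey the right size for these two contrasts, and a matched method gives the same protection with more power.

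**Conclusion.** The point holds as a mismatch between method and contrasts. On the best reading, the plan's secondary tests at T2 and T3 run at about 2% familywise error where 5% is allowed. Relative to a two-contrast method, the cost at 107 per arm is about 13-15 points of power at 0.29 SD, 11-12 at 0.36 SD and 3 at 0.50 SD; at 81 per arm and 0.36 SD it is about 13-15 points.

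The critical values follow from the method and the count of means. The power figures rest on the assumed 1:1 split and on T4 inputs carried over to T2 and T3; the error figures rest on an assumed correlation between visits. The consequence is confined to which secondary visit-specific results are called significant. The primary T4 anxiety contrast, all effect estimates and the sample size stay as they are.

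**What to change.** In Section 6.0, Aim 1 Analysis:
- Replace the Tukey method with Holm, applied within each caregiver outcome score to the arm contrasts at T2 and T3 from the mixed model, at familywise 0.05. A multivariate-t adjustment of the same two contrasts is an equivalent option, but the text should commit to one.
- Keep the T4 anxiety contrast separate at 0.05.
- For depression, HRQOL and fatigue, Section 6.1 lists only T2 and T3, although Table 4 also has them measured at T4. State that the family is the two contrasts, or put T4 in the same Holm family if it will be tested.
- State whether global physical and global mental health, both produced by the caregiver HRQOL scale (Section 5.2), count as one outcome or two.

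The cost is one or two lines of SAP text and one option in the analysis code. Nothing changes in data collection or enrollment.

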We estimate, based on the annual Cancer Registry data, that 131 patients with stage I, II, III rectal, anal, and esophageal cancers; stage III NSCLC; and stage I-IV A/B HNC will be receiving radiation therapy at the three study sites of the Cancer Center. Approximately 10% of these patients will not meet our eligibility criteria (e.g., no family CG), resulting in 118 potential participants annually. Based upon our current pilot study, *Building Family CG Skills Using a Simulation-Based Intervention for Care of Patients with Head and Neck Cancer*, we expect a CG refusal rate of 40%. Therefore, we project to enroll 71 CGs per year or 5 per month. We plan to enroll subjects for 36 months, resulting in an enrollment of 180 subjects over the course of the study. We will allow for a 10% dropout rate, resulting in 162 subjects for the final analysis. The estimated 10% attrition rate is based on a current caregiver intervention study in the Cancer Center, in which the rate is 9.7% (NR015464, [name] PI).

While 40% is a high refusal rate, it is consistent with other intervention studies that aimed to enroll patient-caregiver dyads.^{2,3,90} In addition, the use of incentives has been found to reduce the refusal rate in this CG population, and thus, we will offer a \$100 incentive to all CGs for participation in the study. We will also seek IRB approval to collect additional information from CGs who refuse, including whether the CG is working and/or providing care to other individuals, which were common reasons for refusal in the pilot study. Lastly, we will monitor the refusal rate monthly. If the refusal rate is greater than 40% for more than 4 months, we will consider revising our strategies and seek other sites. We will offer a \$40 incentive to all patients for participation in the study.

For the extension period, with the increased number of study sites we project to enroll 6 caregivers per month. We plan to enroll subjects for an additional 16 months, resulting in 96 subjects over the course of the extension project. We project that the parent study will enroll a total of 148 subjects. Adding the 96 subjects in the extension project will result in a total sample size between the parent study and extension project of 244. With an estimated dropout rate of 12%, the sample for the final analysis will be 214 dyads.

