Power. Analyses for Aim 4 to examine moderating effects will be primarily exploratory in nature, since it is well-recognized that power for testing interaction effects is not high in trials that are powered to detect main effects, as is the case here.¹¹² When testing interaction of a binary factor occurring with frequency 0.5, power is 0.86 to detect an interactive effect size of 1.0 SDs (e.g., an intervention effect of 1.0 in one subgroup and an effect of 0.0 in the other), using a 2-sided test, significance level 0.05.

Aim 4a: Analyses for Aim 4a will examine if the SDH variables moderate the relationship between the intervention and caregiver outcomes. Effects of potential modifiers of the treatment effect will be examined by including terms for the SDH modifier by treatment interaction effect in the basic ANCOVA model used to test the primary hypothesis. The increase in enrollment from the extension study will provide additional power, as it is well-recognized that power for testing interaction effects is not high in trials that are powered to detect main effects, as was the case with the parent study. When testing interaction of a continuous SDH modifiers and the treatment, power is 0.81 to detect an interactive effect size of 0.40 standard deviations (SD) using a 2-sided test, significance level 0.05, for those measures that will be available in all subjects (e.g. Ohio Opportunity Index). For SDH measures that will only be available in the 96 extension study participants, we will be able to detect an interactive effect size of 0.59 at the same power and significance levels.

Aim 4b: Qualitative interviews will be audio recorded and transcribed, then verified for accuracy by research staff. Any identifiable information will be removed from transcripts, and each will be assigned a

study number. Deidentified data will be analyzed with NVIVO software using thematic analysis. First, the research team, including the PI, will read and reread 5 transcripts to develop a codebook using an inductive approach. Then, all transcripts will be coded by the research team using NVIVO to organize the data. Additional codes, and subsequently categories of codes will be identified. Clusters of categories converged into themes. Each transcript will be read and coded by three members of the research team for interrater reliability.

Aim 5

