Analysis. We will assess costs associated with healthcare utilization in both intervention and control groups. Medicare reimbursement rates will be used to estimate costs regardless of the age or insurance of the participant. Using the DRG, diagnosis and procedure codes we will determine what Medicare “would have paid” for those services, and will use that as a proxy for cost. Cost of IV fluids will be estimated using wholesale acquisition cost. We will compute a healthcare utilization cost for each participant. Mean differences between the two groups will be analyzed using a two sample *t*-test for independent means. If necessary, data will be transformed to satisfy normality. In addition, we will describe costs associated with the intervention. Data regarding nurse time for preparation of the simulation and delivery of the intervention (in-person and phone contacts) will be collected prospectively during the study period. An hourly cost will be estimated according to hourly rates according to the Wage and Compensation Survey of the Bureau of Labor Statistics. Equipment costs will be measured. We will also determine costs related to the participants. CGs will be surveyed at each intervention contact (during radiation weeks 1 and 3, and at the end of radiation treatment) regarding: (1) any travel expenses for meetings with the intervention nurse and (2) time lost from work and activities due to the intervention, valued at 100% and 60% of the average hourly rate.

Power. A sample size of 81 in each group will provide 90% power of detecting a medium effect size (Cohen's $d=0.5$) difference between the two means. A two-tailed Type I error rate of 0.05 will be assumed.

In summary:

(1) For the power calculation, we focused on our primary hypothesis and outcome in Aim 1 to determine the sample size for our study ($n=162$); for the rest of other 4 Aims, we assessed the powers based on the sample size obtained in Aim 1. We showed that the proposed sample size will provide clinical meaningful effect size with enough statistical power for all the aims we planned to investigate;

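### The Aim 1 detectable effects (0.36 SD adjusted, 0.41 SD unadjusted) do not follow from 81 per arm, and most power statements still assume 162 analysed when the plan is now 214

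*Combined protocol and SAP*

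**What the plan says.** The Aim 1 power paragraph in Section 6.2 fixes the sample: "With 180 subjects randomized and a 10% dropout rate, the sample size for the primary analysis will be 162 CGs (81 per arm"). It assumes a correlation of 0.50 between baseline and T4 anxiety, a two-sided 0.05 test and 80% power. It reports a detectable difference of 0.36 within-group SDs at T4, explaining that "adjustment for baseline anxiety reduces the detectable effect size from 0.41 to 0.36". The unadjusted value is then carried over to the remaining endpoints: "For other outcomes, there is 80% power to detect effect sizes of 0.41".

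Other parts of Section 6 use the same sample. Aim 2 says that "sample sizes of 81 patients per group will provide 80% power to detect a 68% reduction in unplanned missed days". Aim 5 says that "A sample size of 81 in each group will provide 90% power of detecting a medium effect size". The closing summary gives n=162 as the size set by Aim 1 and adds that "for the rest of other 4 Aims, we assessed the powers based on the sample size obtained in Aim 1".

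Section 3.0 (Projected Enrollment) gives a larger plan: "Adding the 96 subjects in the extension project will result in a total sample size between the parent study and extension project of 244". It then applies 12% dropout to reach 214 dyads for the final analysis. Section 1.1 also gives 244. Within the power statements, only Aim 4a takes up the change: "The increase in enrollment from the extension study will provide additional power".

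**The concern.** There are two separate problems.

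- **Arithmetic.** Every input to the Aim 1 calculation is stated, so the detectable effects can be checked directly, and they come out larger than the plan says. The 0.41 is also the only power figure offered for the other caregiver outcomes, so the error extends beyond the primary endpoint.
- **Sample size.** The current text contains two analysis sample sizes for the primary comparison, 162 and 214. A reader of Section 6 alone would take 162 as the planned primary-analysis sample.

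What is at stake is the stated justification for the primary endpoint. The plan claims 80% power where its named sample gives about 74 to 75%. It also supports the target effect by calling 0.36 close to a pooled estimate of 0.29 from a meta-analysis. The correct value at 162 (0.38) is further from 0.29, and the value at 214 (0.33) is nearer.

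**Working it through.** **Inputs.** From Section 6.2, Aim 1: n = 81 per arm, two-sided alpha 0.05, power 80%, correlation r = 0.50, effects in units of the within-group SD at T4. From Section 3.0: 244 enrolled, 12% dropout, 214 analysed. Equal arms of 107 are an assumption, because no per-arm figure is given for 214.

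**Dropout.** 180 × 0.90 = 162, as stated. 244 × 0.88 = 214.7, which agrees with 214.

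**Formula (normal approximation).** Detectable d = (1.960 + 0.842) × sqrt(1 − r²) × sqrt(2/n), with r = 0 when unadjusted.

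- 81 per arm, unadjusted: 2.802 × sqrt(2/81) = 2.802 × 0.1571 = 0.440. The plan states 0.41.
- 81 per arm, adjusted: 0.440 × sqrt(0.75) = 0.440 × 0.866 = 0.381. The plan states 0.36.
- The adjustment step itself is sound: 0.41 × 0.866 = 0.355. The discrepancy is already present in the 0.41.

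**Noncentral t** (one degree of freedom spent on the covariate in the adjusted case):

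| Total (per arm) | Detectable, unadjusted | Detectable, adjusted | Power at 0.41 unadjusted | Power at 0.36 adjusted |
|---|---|---|---|---|
| 148 (74) | 0.464 | 0.402 | 69.8% | 71.0% |
| 162 (81) | 0.443 | 0.384 | 73.7% | 74.8% |
| 180 (90) | 0.420 | 0.364 | 78.1% | 79.2% |
| 214 (107) | 0.385 | 0.333 | 84.7% | 85.7% |
| 244 (122) | 0.360 | 0.312 | 89.1% | 89.9% |

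For 80% power, 0.41 unadjusted needs 95 per arm and 0.36 adjusted needs 92 (94 and 91 by the normal approximation).

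**Attempts to recover the stated figures.**

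- Rounding: at 81 per arm, even 0.4149 and 0.3649 give only 74.7% and 76.0% power.
- One-sided 0.05 at 81 per arm (normal approximation): 0.391 and 0.338, neither of which matches.
- A higher correlation: 0.36 at 81 per arm would need r of about 0.58, and this could not affect the unadjusted 0.41.
- All 180 before dropout: 0.364 adjusted rounds to 0.36, but 0.420 unadjusted does not round to 0.41.

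**Aim 5.** At d = 0.5, power is 88.5% with 81 per group (stated 90%) and 95.4% with 107.

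**The case against.** The best defence has four parts.

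1. **The figures may come from the 180 randomised.** At 90 per arm the normal approximation gives 0.4176 and 0.3617, which become 0.41 and 0.36 if truncated. This is a plausible origin, though the documents do not confirm it. It does not rescue the text, which attributes the figures to 162 after dropout, and 0.4176 rounds to 0.42.

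2. **A careful reader can tell the two stages apart.** Section 3.0 gives the 180/162 plan first and introduces 244/214 as the extension. Aim 4a also refers back to the parent study as powered for main effects. That helps, but the Aim 1 paragraph and the summary carry no such label and speak of 162 as the sample to come. Section 3.0 now projects 148 from the parent study, so 180 is no longer the parent projection either.

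3. **The basis of Aims 3 and 4 is less clear.** Neither paragraph states an n, and only the summary sentence ties them to 162. For Aim 4, an interaction of 1.0 SD with four equal cells has a standard error of sqrt(4/37) = 0.329 at 148 in total, giving power of about 86%, the stated value. At 162 it is sqrt(4/40.5) = 0.314, giving about 89%. It is therefore safer to say that the summary implies 162 for these aims.

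4. **The consequence is small.** An error of 0.02 to 0.03 SD, with the pilot anxiety SDs of 9.5 to 11.3 in Table 1, is about 0.2 to 0.3 T-score points. The 1.5-point gap in Aim 5 is minor. Both points stand, and they make this a correction to the justification rather than a challenge to the design.

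**Conclusion.** The concern holds in both parts. The stated 80% overstates power at 81 per arm by about 5 to 6 percentage points, and the detectable effects are understated by 0.02 SD (adjusted) and 0.03 SD (unadjusted). The Aim 1, 2 and 5 statements and the summary were not brought up to the 214 now planned.

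The enlarged trial exceeds 80% power for both stated effects. This rests on equal allocation, the plan's r = 0.50, and a baseline-adjusted comparison at T4. No gain is credited for the T2 and T3 measurements or for other covariates, because the documents give no correlations for them. High confidence; this should be corrected.

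**What to change.** - **Aim 1:** state that, with 244 enrolled, 12% dropout and 214 analysed (107 per arm, 1:1 assumed), there is 80% power for 0.33 SD adjusted for baseline at r = 0.50 and 0.38 SD unadjusted. Use 0.38 SD for the other outcomes, and name the calculation method.
- **Parent-study calculation:** if the 162-based figures are kept for the record, label them as the parent-study basis and correct them to 0.38 SD adjusted and 0.44 SD unadjusted. Presenting the 214-based figures as current power, beside the labelled original, avoids implying that 244 was chosen for Aim 1.
- **Summary:** replace or label n=162.
- **Aim 5:** restate at 107 per group (about 95% power at d = 0.5).
- **Aims 2 and 3:** rerun at the current sample with the plan's own Poisson and mediation methods. No replacement values are offered here because they depend on the exact tests used. State the n behind Aims 3 and 4.

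The cost is a short recalculation and some wording. The endpoint, test, allocation and enrolment target are unchanged.

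### The Aim 2 patient HRQOL model treats T1 as an outcome and states neither a baseline covariate nor a common T1 mean, so it may give up precision that the collected baseline offers

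*Combined protocol and SAP*

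**What the plan says.** The combined document sets out two different treatments of baseline in section 6.0.

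- **Caregiver anxiety (Aim 1, Analysis).** The outcomes are changes at T2, T3 and T4, modelled "using baseline anxiety as a covariate, also adjusting for covariates described in Table 4". The arm contrast at T4 is named as the primary test. The approach is then carried over to the remaining caregiver measures: "Other CG outcomes will be compared between groups using a similar approach". Patient measures are not mentioned there.
- **Patient HRQOL (Aim 2, Analysis).** The whole model statement is: "HRQOL, a continuous measure, will be analyzed using a linear mixed model with repeated measures at T1, T2, T3, and T4". T1 is one of four outcomes. The text does not give the mean structure, say whether the arms may differ at T1, or name the contrast to be tested.

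Section 6.1 lists patient HRQOL as a secondary endpoint at the end of treatment (T2) and at 4 weeks after treatment (T3). Table 4 has FACT collected at all four times. Section 4.0 places baseline collection before random assignment.

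The Aim 1 power paragraph credits adjustment with a gain: "adjustment for baseline anxiety reduces the detectable effect size from 0.41 to 0.36". It quotes 0.41 SD for all other outcomes. The Aim 2 power paragraph covers only missed days and hospital admissions and says nothing about HRQOL.

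**The concern.** A mixed model with T1 to T4 as outcomes is usually fitted with arm, visit and their interaction. Coded that way, each arm has its own free mean at T1. With complete data, the arm contrast at a later visit is then either the plain difference at that visit or the difference in change from T1. Neither uses the T1 score as efficiently as a covariate does.

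Minimization balances caregiver gender, caregiver age and cancer type, but not baseline FACT, so chance differences in FACT at T1 can remain. Given an observed T1 difference and equal variances, a post-only contrast carries a share rho of it. A change contrast over-corrects by a share 1 − rho. At rho = 0.50 each is half the difference.

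What is at stake is precision for the main patient-reported outcome, together with a choice between contrasts that the plan leaves open.

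**Working it through.** **Inputs**

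| Input | Value | Source |
|---|---|---|
| Test | two-sided 0.05, 80% power | Section 6.0, Aim 1 Power |
| Analysed | 162, or 81 per arm | Aim 1 Power (180 randomized, 10% dropout) |
| Analysed after extension | 214 dyads; 107 per arm if allocation is 1:1 | Section 3.0, Projected Enrollment |
| Baseline to follow-up correlation | 0.50, for caregiver anxiety at T4 only | Aim 1 Power |
| Correlation for FACT | not given; 0.3 to 0.8 assumed | assumption |

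**Step 1: the plan's own figures.** Detectable difference in SD units = (1.960 + 0.842) × √(2f/n), where f is the variance of the contrast relative to an unadjusted one.

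- 81 per arm: 2.8016 × √(2/81) = 0.440 unadjusted (f = 1). With f = 1 − 0.50² = 0.75, it is 0.440 × 0.866 = 0.381.
- 90 per arm (all 180, no dropout): 0.418 and 0.362.

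The stated 0.41 and 0.36 do not reproduce at 81 per arm, where power is 74.2% and 75.4%. They match about 90 per arm. That is a separate matter. The step between them does agree with baseline adjustment at rho = 0.50, since 0.41 × 0.866 = 0.355. The figures below use 0.440 and 0.381.

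**Step 2: relative variance of the arm contrast at one later visit**, with equal variances at T1 and that visit:

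- T1 as outcome, free arm means, post-only contrast: 1
- T1 as outcome, free arm means, change contrast: 2(1 − rho)
- T1 as outcome, common T1 mean: 1 − rho²
- T1 as covariate: 1 − rho²

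Generalized least squares on four visits with equal correlation returned exactly these values. A simulation of 20,000 trials at 81 per arm and rho = 0.50 gave covariate-adjusted variance ratios of 0.76 against post-only and 0.75 against change.

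The saving from adjustment is therefore rho² against post-only, and 1 − (1 − rho²)/[2(1 − rho)] = (1 − rho)/2 against change.

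**Step 3: over the assumed range, 81 per arm**

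| rho | Saving vs change | Saving vs post-only | Detectable SD: post-only | change | adjusted |
|---|---|---|---|---|---|
| 0.3 | 35% | 9% | 0.440 | 0.521 | 0.420 |
| 0.4 | 30% | 16% | 0.440 | 0.482 | 0.403 |
| 0.5 | 25% | 25% | 0.440 | 0.440 | 0.381 |
| 0.6 | 20% | 36% | 0.440 | 0.394 | 0.352 |
| 0.7 | 15% | 49% | 0.440 | 0.341 | 0.314 |
| 0.8 | 10% | 64% | 0.440 | 0.278 | 0.264 |

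At 107 per arm and rho = 0.50, the detectable difference is 2.8016 × √(2/107) = 0.383 unadjusted and 0.332 adjusted. Matching the adjusted precision without adjustment would take 1/0.75 = 1.33 times as many patients.

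With a common T1 mean the variance equals that of the covariate model at every rho in the table, so the loss is then zero.

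**The case against.** The strongest reply is that the plan is silent here rather than wrong. A constrained longitudinal model, with T1 as an outcome and one T1 mean for both arms, also fits the Aim 2 sentence, and it loses nothing. This stands. A reader might infer that the plan definitely discards baseline information, but the text neither states nor rules out the constraint, so the loss is conditional.

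The 0.50 is also borrowed: "Assuming a correlation of 0.50 between CG anxiety scores at baseline and T4" concerns another person, another instrument and a later visit than the patient HRQOL endpoints. This stands too, and it is why the range is shown.

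A reader might take the 0.41 SD given for other outcomes as evidence that HRQOL will not be adjusted. It does not show that. The same figure covers the other caregiver outcomes, which are to follow an approach similar to Aim 1.

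A reader might also fear a single arm effect averaged over T1 to T4, diluted by a visit at which no effect can exist. No such effect is proposed, and section 6.1 names visit-specific endpoints, which points the other way.

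Finally, no stated HRQOL power depends on adjustment, because the plan makes no HRQOL-specific power claim. That limits the consequence but does not remove the gap in the specification.

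**Conclusion.** The point holds as a gap in specification with a conditional cost in efficiency. If T1 arm means are left free, the later-visit contrast is less precise than a baseline-adjusted one at every correlation examined. At an assumed rho of 0.50, about a quarter of the variance is given up, which is all of the reduction that adjustment offers at that value. If the means are constrained equal at T1, nothing is lost.

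The sizes rest on equal variances across visits, complete data, 1:1 allocation for the 107 per arm, and an assumed FACT correlation.

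A reader might go further and infer bias or an inflated type I error. The documents do not support that: in this randomized comparison both unadjusted contrasts are unbiased over repeated randomization, and a chance T1 difference adds variance only. Patient HRQOL is a secondary endpoint, so this is a worthwhile free improvement and no threat to the primary analysis.

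**What to change.** In section 6.0, Aim 2, replace the HRQOL model statement with one of two equivalent specifications:

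1. FACT at T2, T3 and T4 as outcomes, with arm, visit, their interaction, and T1 FACT as a covariate.
2. FACT at T1 to T4 as outcomes, with a single T1 mean common to both arms and arm-specific means afterwards. This version retains patients whose T1 score is missing.

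Then name the tests: the arm contrasts at T2 and T3, the visits in section 6.1, with T4 as additional.

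The cost is SAP wording only. T1 FACT is already collected before randomization, and no extra visits, data or patients are needed.
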